5.2 Preparation, Administration, and Dosage of Study Agent

The dose of 10-1074 for this study is 30 mg/kg in 250 mL normal saline with overfill (20 mL). The dose of VRC01 is 40 mg/kg in 100 mL of normal saline. The placebo will be matching volumes of normal saline alone. The two antibodies will be mixed in separate bags of saline for sequential administration.

To prepare an IV infusion of 10-1074, the pharmacist will calculate the total milligrams of each antibody needed and add the calculated total milligrams needed to a 250 mL of normal saline with 20 mL overfill using good pharmacy practices to maintain sterility. The infusion solution must be used within 3 hours. Any unused portion of an antibody vial will not be used for another subject.

To prepare an IV infusion of VRC01, the pharmacist will calculate the total milligrams needed, retrieve the minimum number of thawed, particle free vials needed to prepare the full dose and add the calculated total milligrams needed to a 100 mL bag of normal saline using good pharmacy practices to maintain sterility (details for thawing vials are provided in the IB, Section 6.1.1). Prior to preparation for administration, vials should be gently swirled for 30 seconds, avoiding foaming. DO NOT SHAKE THE VIALS. Typically, 50 to 100 mL of additional volume may be added to a 100 mL bag of normal saline. The pharmacist should test the capacity of the brand of saline bags that will be used at the site to confirm the capacity to add this additional volume. After product preparation in IV bags, the prepared VRC01 may be stored at 2°C to 8°C up to 24 hours or at room temperature (maximum 30°C) for a maximum of 8 hours total including the infusion time.

The antibodies (or normal saline placebo) will be administered sequentially by IV infusion (10-1074/placebo first, followed by VRC01/placebo). Each infusion will be given over 60 minutes using a volumetric pump and then the line will be flushed with 20 mL normal saline. The total time needed to administer the dose may be longer than 60 minutes based on factors such as subject tolerance.

For women of childbearing potential, study agent administration may not proceed unless a negative pregnancy test has been obtained within the previous 24 hours. Vital signs (temperature, blood pressure, heart rate) will be measured 30 minutes into the infusion and at the end of the infusion. Following the completion of the VRC01/placebo infusion, the subject will be observed for 30 minutes and vital signs will be taken before the subject leaves the clinic.

5.2.1 Dose Adjustments and Modifications

Mild-moderate infusion related symptoms (Grade I-II), should they develop, will be managed by temporarily stopping the infusion until symptoms have resolved. For symptoms such as fever, myalgia, or urticaria, symptomatic treatment with standard doses of acetaminophen, ibuprofen, or antihistamines may be given. Once symptoms have resolved, the infusion will be restarted at a reduced rate. If symptoms recur following a reduced infusion rate and symptomatic treatment, the infusion will again be stopped until symptoms resolved and restarted at a lower rate. If the infusion cannot be completed within a 3-hour (10-1074) or 8-hour (VRC01) time frame because of recurrent symptoms, the infusion(s) will be discontinued and the subject will be monitored/treated as may be clinically indicated until deemed to have reached a stable and appropriate condition for discharge/departure.

5.3 Concomitant Medications and Procedures

All concomitant prescription medications taken during study participation will be recorded in Clinical Research Information Management System of the NIAID (CRIMSON). For this protocol, a prescription medication is defined as a medication that can be prescribed only by a properly authorized/licensed clinician. Medications to be reported in CRIMSON are concomitant prescription medications, over-the-counter medications, and non-prescription medications taken at the time of AEs (all grades).

5.4 Prohibited Medications and Procedures

Treatment with immunosuppressive medications during the study is prohibited. Prohibited immunosuppressive medications do not include [1] corticosteroid nasal spray or inhaler; [2] topical corticosteroids for mild, uncomplicated dermatitis; or [3] oral/parenteral corticosteroids given for non-chronic conditions not expected to recur with a length of therapy \leq 10 days.

6 STUDY SCHEDULE

For all the study visits, unless otherwise specified, subjects will come to the NIH CC to undergo the procedures. Unless otherwise specified, the visit window for the post-entry study visits is \pm 5 days.

6.1 Screening

Screening may occur over the course of several contacts/visits. All inclusion and exclusion criteria must be assessed within 8 weeks before enrollment, unless otherwise specified in the eligibility criteria.

After signing informed consent, subjects will undergo the following procedures:

- Medical history and physical examination, including weight and vital signs.
- Assessment of concomitant medications
- Blood collection for:
 - HBsAg and Hepatitis C antibody serology
 - Complete blood count (CBC) with differential, prothrombin time (PT), activated partial thromboplastin time (aPTT)
 - Chemistry panel to include: alanine transaminase (ALT), aspartate aminotransferase (AST), alkaline phosphatase (ALP), creatinine, total and direct bilirubin, and serum albumin levels
 - Flow cytometry panel (includes CD4+ cell count)
 - Plasma HIV and HCV viral RNA levels
- Storage of serum and plasma (if needed for repeat HIV antibody testing or viral RNA levels)
- Urinalysis
- Serum or urine pregnancy test for women of child-bearing potential

Subjects taking NNRTI-based regimens will be asked to switch to a Protease or Integrase-based regimens at least 2 weeks before returning for Enrollment/Baseline visit.

6.2 Enrollment/Baseline

Participants will undergo the following procedures:

- Medical history and physical examination, including weight and vital signs
- Assessment of concomitant medications
- HIV transmission risk behavior assessment and counseling
- Blood collection for:
 - Flow cytometry panel (includes CD4+ cell count)
 - Plasma HIV viral RNA levels
 - Human leukocyte antigen (HLA) typing (if not already on file)
 - Storage of plasma, serum and peripheral blood mononuclear cells (PBMCs)
 - CBC with differential
 - Chemistry panels, to include: ALT, AST, ALP, creatinine, total and direct bilirubin, and serum albumin levels
 - Serum or urine pregnancy test (women of child-bearing potential)

6.3 First ATI Phase

The day following the enrollment visit, the participants will be instructed to stop their ART.

Storage of plasma, serum, and cells may be done at ATI Week 2, 4 and every 2 weeks thereafter for the duration of the first ATI phase. Flow cytometry (including CD4 count) and plasma HIV viral RNA levels will be done every 2 weeks for the duration of the ATI Phase. HIV genotype will be obtained on all samples with HIV viral levels >1,000 copies/mL. For select participants residing outside the local (Bethesda, MD) area, blood samples for blood draw only visits, may be collected at their local clinics or Quest Diagnostics and sent to the NIH CC for

testing. Samples collected at clinics or at Quest may be labeled with a coded identifier, gender, and date of birth, as required by the local facility.

During the first ATI Phase, participants will be evaluated at the CC outpatient clinic every 4 weeks. At these clinic visits, the following will be done in addition to the flow cytometry panel and plasma HIV viral level:

- Interval medical history and a targeted physical examination, including weight, vital signs, and a symptom-directed evaluation based on symptoms or complaints reported by each subject
- Assessment of concomitant medications
- Assessment of any new or unresolved AEs/intercurrent illnesses
- Blood collection:
 - CBC with differential
 - Chemistry panels, to include: ALT, AST, ALP, creatinine, total and direct bilirubin, and serum albumin levels
 - HIV transmission risk behavior assessment and counseling

For participants who are unable to return to the NIH CC during the COVID-19 pandemic/epidemic due to travel restrictions, blood samples may be collected at their local clinics or Quest Diagnostics and sent to the NIH CC for testing which will include; CBC with differential, plasma HIV viral level, and flow cytometry. Chemistry panels may be collected and run at Quest Diagnostics laboratories with results sent to the NIH. A study provider (Nurse Practitioner, Physician's Assistant, or Physician) will contact participants by phone and obtain an interval medical history.

6.4 Treatment Phase

When a single plasma viral level that is ≥ 200 copies/mL is detected, the participant will return within 14 days for randomization and entry into the Treatment Phase of the study. Following randomization, participants will receive single infusions of 10-1074/placebo and VRC01/placebo given sequentially at the same visit. All participants will be instructed to restart ART the day following study infusions. Participants will be contacted by phone 72 hours after the study infusions to verbally assess for any reactogenicity symptoms (e.g. rash, arthalgias, fever).

During the Treatment Phase of the study, participants will be seen on the day of bNAb/placebo infusion and every 4 weeks thereafter and undergo the following study procedures.

- Interval medical history and a targeted physical examination, including weight, vital signs, and a symptom-directed evaluation based on symptoms or complaints reported by each subject
- Assessment of any new or unresolved AEs or intercurrent illnesses
- Blood collection for:
 - CBC with differential
 - Chemistry panels, to include: ALT, AST, ALP, creatinine, total and direct bilirubin, and serum albumin levels
 - Plasma HIV viral level
 - Flow cytometry panel
 - Storage of serum, plasma and PBMCs

- Serum or urine pregnancy test for women of child-bearing potential (at infusion visit only)

For participants who are unable to return to the NIH CC during the COVID-19 pandemic/epidemic due to travel restrictions, blood samples may be collected at their local clinics or Quest Diagnostics and sent to the NIH CC for testing which will include; CBC with differential, plasma HIV viral level, and flow cytometry. Chemistry panels may be collected and run at Quest Diagnostics Laboratories with results sent to the NIH. A study provider (Nurse Practitioner, Physician's Assistant, or Physician) will contact participants by phone and obtain an interval medical history.

6.5 Second ATI Phase

The second ATI Phase will begin after the participant's plasma viral level reaches <40 copies/mL and is sustained at this level for 12 weeks. Blips of low-level viremia during this period will be allowed provided these "blips" are <400 copies/mL and succeeding viral levels return to <40 copies/mL on subsequent testing. After 12 weeks of sustained suppression of plasma viremia, the participant will stop ART and be monitored as described in [Section 6.3](#). Participants will remain off ART until they meet one or more of the ART restart criteria described in [Section 3.1](#).

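### In the narrative, the second ART stop requires no pregnancy test after the infusion visit, at least about 15 weeks earlier; the first stop follows a test by one day

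*Combined protocol and SAP*

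**What the plan says.** **Tests required in the narrative.** There are three: at screening (Section 6.1), at enrollment (Section 6.2: "Serum or urine pregnancy test (women of child-bearing potential") and at infusion. Section 5.2 requires the infusion test to be negative within 24 hours before dosing. Section 6.4 confines Treatment Phase testing to that one visit: "Serum or urine pregnancy test for women of child-bearing potential (at infusion visit only".

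**First ART stop.** Section 6.3: "The day following the enrollment visit, the participants will be instructed to stop their ART".

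**Visits between infusion and the second stop.** Section 6.4: "participants will be seen on the day of bNAb/placebo infusion and every 4 weeks thereafter", with blood drawn each time. Section 6: "Unless otherwise specified, the visit window for the post-entry study visits is" ±5 days.

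**Second ART stop.** Section 6.5: "After 12 weeks of sustained suppression of plasma viremia, the participant will stop ART and be monitored as described in" Section 6.3. The only condition is 12 weeks below 40 copies/mL, with small blips allowed. Section 6.3 lists no pregnancy test among its monitoring procedures, and neither does the Follow-up Phase in Section 6.6.

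**Status of pregnancy.** Section 3.1 makes it a criterion to restart ART in the second ATI. Sections 12.4.4 and 12.9 make it a reason for withdrawal.

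**Other safeguards.** Section 4.2 requires effective contraception throughout, condoms while off ART, barrier methods or abstinence during the ATI, and prompt reporting of a suspected pregnancy. The 4-weekly ATI clinic visits in Section 6.3 include transmission-risk counseling, an interval history and a targeted examination with "a symptom-directed evaluation based on symptoms or complaints reported by each subject".

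**The concern.** The protocol treats pregnancy as incompatible with being off ART in the second ATI, yet the narrative has no step that would find an unrecognised pregnancy before ART is stopped. It does have such a step before the first stop and before the infusion. A woman who conceives during the months on ART after infusion could meet the suppression rule, stop ART and become viremic before anyone suspects a pregnancy.

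What is at stake is the safety of the participant and the fetus. The point makes no claim about power or bias.

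**Working it through.** The documents give no figure for the age of the last test, so there is none to reproduce. The check is calendar arithmetic.

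**Inputs**
- Enrollment test to first ART stop: 1 day (Sections 6.2, 6.3).
- Infusion-visit test: taken as day 0. Section 5.2 allows it to be up to 24 hours older.
- Visits every 4 weeks = 28 days (Section 6.4); window ±5 days (Section 6).
- Suppression required: 12 weeks = 84 days (Section 6.5).
- Control median time to restart criteria: 39.486 days (Section 14).
- Sample size 50, accrual ceiling 75 (Protocol Summary).

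**Formula.** Age of last required test at the second stop = day of first on-ART value below 40 copies/mL + 84.

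| First value <40 copies/mL | Nominal | With visit 5 days early |
|---|---|---|
| Week 4 | 28 + 84 = 112 d = 16.0 wk | 23 + 84 = 107 d = 15.3 wk |
| Week 8 | 56 + 84 = 140 d = 20.0 wk | 51 + 84 = 135 d = 19.3 wk |
| Week 12 | 84 + 84 = 168 d = 24.0 wk | 79 + 84 = 163 d = 23.3 wk |

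The documents do not say how long re-suppression takes, so the week 4 row is the minimum and the others show the range. A value below 40 at the infusion visit itself would not start the clock, because Section 3.1 counts suppression induced by the restarted ART.

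**Sensitivity.** Counting the 4 weeks from ART restart (day 1) gives 24 + 84 = 108 days = 15.4 weeks. Applying the early window again at the end of the 12 weeks gives 23 + 79 = 102 days = 14.6 weeks. The wording of Section 6.5, which asks for 12 weeks of sustained suppression, does not support that second reading, and it would not change the conclusion.

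**Missed opportunities.** On the nominal schedule, up to the earliest stop there are four visits after infusion (weeks 4, 8, 12 and 16) at which blood is drawn and no pregnancy test is listed.

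**During the second ATI.** At the control median, the last required test is at least 107 + 39.486 = 146.5 days = 20.9 weeks old. At ATI week 16 it is at least 107 + 112 = 219 days = 31.3 weeks old.

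**Remote visits.** Under the COVID-19 provisions in Sections 6.3 and 6.4, a study provider "will contact participants by phone and obtain an interval medical history", and the listed local blood tests do not include a pregnancy test.

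**The case against.** **Appendix A may schedule the test.** It has a pregnancy row, a column for the last ART dose and columns for the second ATI. The table was available only in a broken form that has lost marks: even the infusion-visit test, which Sections 5.2 and 6.4 require, is not shown. A reader might infer that no test is scheduled anywhere in the second ATI. The documents do not support that, and the point is confined to the narrative. Section 6.4 does speak against a further Treatment Phase test, because it limits testing to one visit, but it says nothing about the ATI visits.

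**The other safeguards are substantial.** Contraception, barrier use or abstinence while off ART, counseling, history and self-report all apply in the window at issue and lower the risk. This stands. However, the study-long contraception rule also covers the first ART stop and the infusion, where the protocol still tests. History, examination and self-report help only once a pregnancy is suspected.

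**Test age is not risk.** This stands too. The documents give neither the number of women of childbearing potential nor a pregnancy rate. A reader might take 15 or 31 weeks as a measure of how often harm would occur, but it is only the length of the untested interval.

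**The contrast with the first stop is partly structural.** The enrollment test also helps to confirm eligibility. That explains why a test falls there, but not why none is required before the second stop.

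**Conclusion.** The point holds as a narrow participant-safety gap in Sections 6.4 and 6.5, and it should be fixed. The last required test is 1 day old at the first ART stop. At the second it is at least 107 days old (15.3 weeks; 16 weeks nominal).

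This rests on suppression first seen at the week 4 visit and on a full 84 days of suppression. Later suppression lengthens the interval. It also assumes that Appendix A carries no mark at the last ART dose. If it does, the safety gap is smaller and the task is mainly to align the narrative, because neither Section 6.4 nor Section 6.5 makes a negative result a condition for stopping.

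The number of affected participants is expected to be small and cannot be derived. Because pregnancy is a restart criterion, and so part of the primary endpoint, a reader might also infer bias or lost power. Nothing in the documents supports a count or an imbalance between arms, so neither is claimed.

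**What to change.** - **Section 6.4:** replace the restriction to the infusion visit with *at the infusion visit and at the last visit before ART is stopped for the second ATI*.
- **Section 6.5:** for women of childbearing potential, require a negative serum or urine pregnancy test at that visit, in addition to 12 weeks of suppression, before ART is stopped.
- **Remote visits:** add the test to the local sample collection.
- **Appendix A:** mark the test if it is not already there.
- **Positive result:** the participant stays on ART, is handled under Sections 12.4.4 and 12.9 with safety follow-up, and is reported by arm as having no second ATI and therefore no primary-endpoint time.
- **Reasonable addition:** repeat the test at the existing 4-weekly ATI clinic visits. The single test before the stop cannot detect conception during the interruption; repeat tests are needed for that.

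**Cost.** Amendment wording and one inexpensive test per woman of childbearing potential, of a kind already in use and at an existing visit. The ceiling is 1 × 50 = 50 tests, or 1 × 75 = 75 at the accrual ceiling, even if every participant were such a woman. Repeat testing through ATI week 16 would add up to 16 / 4 = 4 tests each. The other downside is a rare randomised participant without a second ATI.

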6.6 Follow-up Phase

When participants meet criteria to restart ART, they will restart treatment and enter the Follow-up Phase. Participants will be seen 4, 12, and 24 weeks after restarting ART to ensure re-suppression of viremia. At each visit participants will undergo the following study procedures.

- Interval medical history and a targeted physical examination, including weight, vital signs, and a symptom-directed evaluation based on symptoms or complaints reported by each subject
- Assessment of any new or unresolved AEs or intercurrent illnesses
- Blood collection for:
 - CBC with differential
 - Chemistry panels, to include: ALT, AST, ALP, creatinine, total and direct bilirubin, and serum albumin levels
 - Plasma HIV viral level
 - Flow cytometry panel to include CD4 count
 - Storage of serum, plasma and PBMCs

For participants who are unable to return to the NIH CC during the COVID-19 pandemic due to travel restrictions, blood samples may be collected at their local clinics or Quest Diagnostics and sent to the NIH CC for testing which will include; CBC with differential, plasma HIV viral level, and flow cytometry. A study provider (Nurse Practitioner, Physician's Assistant, or Physician) will contact participants by phone and obtain an interval medical history.

7 STUDY EVALUATIONS

7.1 Clinical Evaluations

- Participants will undergo a medical history and physical examination.

7.2 **Laboratory Evaluations**

7.2.1 **Clinical and Research Laboratory Evaluations and Specimen Collection**

- HIV viral RNA levels
- HIV genotype (if viral level is >1,000 copies/mL)
- Flow cytometry with CD4⁺ T cell count
- Routine serologic, hematologic, and clinical chemistry evaluations as described in [Section 6](#)

Other research evaluations measuring the effect of VRC01 and 10-1074 on the HIV pathogenesis may include:

- Frequency of CD4⁺ T cells carrying HIV proviral DNA and cell-associated HIV RNA
- Levels of cell-associated infectious virus
- Sequencing of viral DNA and RNA
- Neutralization assays using replication-competent HIV against bNAbs
- Frequency of HIV-specific CD4⁺ and CD8⁺ T cells
- Markers of T-cell activation, immune exhaustion, and inflammation

8 **POTENTIAL RISKS AND BENEFITS**

8.1 **Potential Risks**

General Risks of MAbs Treatment

Administration of mAb may have a risk of immune reactions such as acute anaphylaxis, serum sickness and the generation of antibodies; however, these reactions are rare and more often associated with mAb targeted to human proteins or with the use of chimeric human-murine mAbs, which would have a risk of human anti-mouse antibodies. Both VRC01 and 10-1074 are targeted to a viral antigen (HIV gp120) and are human mAbs; thus, it is expected these mAbs will have a low risk of such side effects. VRC01 and 10-1074 when given individually have both been well tolerated in Phase 1/2 studies with no safety concerns identified.

Typically, the side effects of mAbs are mild but may include fever, chills, rigors, nausea, vomiting, pain, headache, dizziness, shortness of breath, bronchospasm, hypotension, hypertension, pruritus, rash, urticaria, angioedema, diarrhea, tachycardia or chest pain. Most infusion-related events occur within the first 24 hours after beginning administration. Severe reactions, such as anaphylaxis, angioedema, bronchospasm, hypotension and hypoxia, are infrequent and more often associated with mAbs targeted to human proteins or when a nonhuman mAb, such as a chimeric murine mAb, is used.

Delayed allergic reactions to a mAb may include a serum sickness type of reaction, which is characterized by urticaria, fever, lymph node enlargement, and joint pains. These symptoms

may not appear until several days after the exposure to the mAb and is noted to be more common with chimeric types of mAbs.

Analytical treatment interruption (ATI)

The risks from an ATI, performed under close virologic and immunological monitoring are minimal in this subject population. There is a theoretical risk that ATI could lead to the development of HIV drug resistance. This may be a particular concern for individuals taking NNRTIs. However, this potential risk with NNRTIs is essentially eliminated by undertaking the procedures described in [Section 3.1](#). Given the study population, the frequency of immunological and virologic monitoring, and strict criteria for restarting ART, it is extremely unlikely that the ATI will lead to the development of any opportunistic infections or acquired immune deficiency syndrome (AIDS)-defining conditions.

During the ATI phase, participants may transmit HIV infection if they do not adhere to safe sex practices.

Phlebotomy/Insertion of IV Catheter

This may be associated with discomfort, bruising, local hematoma formation and, on rare occasions, infections, lightheadedness, and fainting.

The amount of blood drawn for research purposes will be within the limits allowed for adult participants by the NIH CC (Medical Administrative Policy 95-9: Guidelines for Limits of Blood Drawn for Research Purposes in the Clinical Center: <http://cc-internal.cc.nih.gov/policies/PDF/M95-9.pdf>).

HLA typing

Some HLA types have been associated with an increased risk of certain diseases like arthritis and other rheumatologic disorders, or a faster progression to AIDS. HLA typing will be performed on samples collected from all the enrolled participants. Results from the HLA typing will become part of each participant's medical record at NIH. Medical records containing this information are maintained in a secure place.

